7.6 Population Pharmacokinetic Analysis

Population Pharmacokinetic analysis will be summarized in the “Pharmacokinetic Modeling and Simulation Analysis Plan for AL101 and AL101 Active Metabolite” and is outside the scope of this SAP.

As a part of this SAP PK sample collection data will be presented in a by subject data listing only.

7.7 Exploratory Biomarker Analysis

Exploratory analysis of the correlation between N1CDI staining and Notch1 mutations and the correlation of Notch mutations and associated genes with response or resistance to investigational product will be summarized in the “Biomarker Statistical Analysis Plan.” and is outside the scope of this SAP

Next Generation Sequencing assay results at Screening will be presented in a by subject data listing. Tumor biopsy and blood biomarker sample collection information will also be presented in a by subject data listing only.

7.8 Safety Evaluation

Safety analysis will be carried out for the Safety analysis set, to include all subjects who receive at least one infusion of investigational product, including partial infusions. Subjects who do not complete the study, for whatever reason, will have all available data up until the time of termination included in the analysis. Safety summaries will be presented by dose cohort and with all subjects combined. For safety analysis presented by study visit, the baseline value will be defined as the last value reported prior to first investigational product infusion.

7.8.1 *Extent of Exposure and Treatment Compliance*

Extent of exposure to study treatment will be summarized by dose cohort and over all subjects combined for the Safety analysis set.

The number of infusions attempted, total amount AL101 received (mg) and number of cycles initiated (overall and by subject) will be summarized using descriptive statistics. The number of cycles initiated will also be summarized by the number and percentage of subjects with each number of cycles initiated. The total number of AL101 administrations received as planned and not received as planned will be summarized. The number and percentage of subjects with each reason for infusions not being administered as planned

will also be displayed. The number and percentage of subjects with a planned dose reduction from 6 mg to 4 mg or from 4 mg to 2.4 mg will be presented.

7.8.2 Adverse Events

TEAEs will be summarized by dose cohort and over all subjects combined for the Safety analysis set.

Summaries that are displayed by system organ class and preferred terms will be ordered by descending incidence of system organ class and preferred term within each system organ class. Summaries displayed by preferred term only will be ordered by descending incidence of preferred term.

Summaries of the following types will be presented:

- Overall summary of number of unique TEAEs, treatment-emergent serious adverse events (SAEs) and subject incidence of TEAEs meeting various criteria;
- Subject incidence of TEAEs by MedDRA system organ class and preferred term;
- Subject incidence of TEAEs by MedDRA preferred term;
- Subject incidence of TEAEs by severity grade, MedDRA system organ class, and preferred term;
- Subject incidence of TEAEs related to investigational product, MedDRA system organ class, and preferred term;
- Subject incidence of TEAEs related to investigational product by severity grade, MedDRA system organ class and preferred term;
- Subject incidence of TEAEs Grade ≥ 3 by MedDRA system organ class and preferred term;
- Subject incidence of TEAEs Grade ≥ 3 and related to investigational product by MedDRA system organ class and preferred term;
- Subject incidence of SAEs by MedDRA system organ class and preferred term.
- Subject incidence of SAEs related to investigational product by MedDRA system organ class and preferred term.
- Subject incidence of AESIs by MedDRA system organ class and preferred term.

- Subject incidence of AESIs related to investigational product and MedDRA system organ class and preferred term.
- Subject incidence of TEAEs leading to death by MedDRA system organ class and preferred term.
- Subject incidence of TEAEs leading to drug discontinuation by MedDRA system organ class and preferred term.

At each level of summarization (eg, any AE, system organ class, and preferred term), subjects experiencing more than one TEAE will be counted only once. In the summary of TEAEs by severity grade, subjects will be counted once at the highest severity reported at each level of summarization; in the summary of TEAEs by relationship, subjects will be counted once at the closest relationship to investigational product.

AEs reported with a causality term of “Certain,” “Probable/Likely,” “Possible,” “Conditional/Unclassified” and “Unassessable/Unclassifiable” will be considered to be related to the investigational product and those reported as “Unlikely” will be considered not related.

Adverse event data will be presented in data listings by subject and event.

7.8.2.1 *Adverse Events of Special Interest*

AESIs will be summarized by subject incidence by MedDRA system organ class and preferred term.

AESIs will be presented in a separate data listing.

7.8.3 *Deaths, Other Serious Adverse Events, and Other Significant Adverse Events*

All deaths during the study, including the long-term follow-up period, will be listed by subject, to include the primary cause of death (where applicable). The day of death relative to date of last dose will also be presented. Serious AEs and other significant AEs, including AEs and AESIs that led to withdrawal, interruption, or dose reduction of the investigational product, will be provided in separate subject data listings.

7.8.4 *Clinical Laboratory Evaluation*

Clinical laboratory measurements, including serum chemistry, hematology and coagulation, will be summarized for all subjects in the Safety analysis set by dose cohort and over all subjects combined.

All descriptive summaries of laboratory results will be based on data analyzed by the local laboratory and presented in Système International (SI) units, as suggested by the Center for Biologics Evaluation and Research and the Center for Drug Evaluation and Research Position on Use of SI Units for Lab Tests (Oct 2013). All data will be included in by-subject data listings. Laboratory measurements identified as abnormal (ie, outside the normal range) will also be listed separately by subject, laboratory test, and unit.

Descriptive statistics will be presented for observed values and changes from baseline at each visit where parameters were scheduled to be collected per the clinical study protocol.

Where applicable, hematology, chemistry and coagulation results for select parameters will be assigned a toxicity grade based on the U.S. Department of Health and Human Services Common Terminology Criteria for Adverse Events (CTCAE), version 5.0 (Nov 2017). Five-by-five contingency tables will be presented for lab tests where toxicity grading can be applied to summarize the shift from the baseline grade to the worst postbaseline grade. Grades will be presented as none (Grade 0), mild (Grade 1), moderate (Grade 2), severe (Grade 3), or life-threatening (Grade 4). Death related to AE (ie, Grade 5) cannot be determined with available laboratory-based data collection and, thus, will not be summarized as a category. Summary results will include the count and percentage of subjects within each shift category. Percentages will be based on the number of subjects with baseline and at least 1 post baseline assessment.

Hy's Law will be used to assess subjects for drug induced liver injury. The criteria for Hy's Law is defined as having an ALT or AST result >3 x ULN and Total Bilirubin >2 x ULN and ALP <2 x ULN. The frequency and percentage of subjects meeting criteria will be summarized for each visit.

Urinalysis parameters will be presented in by-subject data listings only.

7.8.5 *Vital Signs, Physical Findings, and Other Observations Related to Safety*

7.8.5.1 *Vital Signs*

Vital signs (including heart rate, respiratory rate, temperature, and blood pressure) will be summarized by dose cohort and over all subjects combined for the Safety analysis set. Descriptive statistics will be presented for results and change from baseline at each visit where parameters were scheduled to be collected.

BMI will be derived as weight (kg) / [height (m)]², based on the collected weight at each visit and height collected at Screening. Descriptive statistics will be presented for results and change from baseline at each visit where parameters were scheduled to be collected.

7.8.5.2 *12-Lead Electrocardiogram*

Twelve-Lead ECG interval parameters of heart rate, PR interval, RR Interval, QRS duration, QT interval, QTcF, and QTcB will be summarized by dose cohort and over all subjects combined for the Safety analysis set. Descriptive statistics will be presented for observed values and changes from baseline at each visit where parameters were scheduled to be collected.

Twelve-lead ECG will be classified by the investigator as “normal,” “abnormal, not clinically significant,” “abnormal, clinically significant.” Three-by-three contingency tables will be presented to summarize the shift from the baseline category to the worst post-baseline value. Summary results will include the count and percentage of subjects within each shift category that had evaluable ECG results. This analysis will be repeated for the central interpretation of the ECGs (central read ECGs do not have clinical significance assigned so only normal/abnormal will be displayed).

Prolonged QTcF and QTcB intervals will be summarized as QTc measurements (msec) that are > 450, > 480, and > 500 at each visit where ECG is routinely collected per the clinical study protocol. Change from baseline categories will also be summarized for measurements that represent a change > 30 or > 60 relative to the baseline value.

7.8.5.3 *ECOG Performance Status*

ECOG exams are to be performed at all study visits.

ECOG will be summarized by dose cohort and over all subjects combined for the Safety analysis set. The shift from the baseline ECOG performance score to the worst postbaseline score will be summarized with the number and percentage of subjects in each shift category for the Safety analysis set (by dose cohort and over all subjects combined). ECOG scores will also be presented in data listings by subject and assessment date.

7.8.5.4 *Physical Examination*

Results of the physical examination will be presented in subject data listings by subject, study visit, and body system.

7.8.5.5 *Prior and Concomitant Medications*

Medications will be coded using the World Health Organization (WHO Drug B3) dictionary. Medications entered on the eCRF will be mapped to Anatomic Therapeutic Chemical (ATC) drug class (level 4) and drug name.

Prior and concomitant medications will be summarized separately and the study phase of each medication will be determined programmatically based on medication start and end dates. A prior medication is defined as any medication administered prior to the date of the first infusion of investigational product. A concomitant medication is defined as any medication administered on or after the date of the first infusion of investigational product. A medication may be defined as both prior and concomitant. If it cannot be determined whether a medication was received prior to the start of investigational product dosing due to partial or missing medication start and/or end dates, it will be considered a prior medication. Likewise, if it cannot be determined whether a medication was received after the start of investigational product dosing, it will be considered concomitant.

For the summary of both prior medications and concomitant medications, the number and percentage of subjects receiving any medication will be summarized for all subjects in the Safety analysis set, as will the number and percentage receiving any medication by ATC drug class and generic drug name. Subjects reporting use of more than one medication at each level of summarization (any medication received, ATC class, and generic drug name) will be counted only once. ATC class terms will be displayed by descending order of incidence, as will generic drug names within each ATC class. The study phase during which each medication was received (eg, prior, concomitant, or both) will be presented on the listing of prior and concomitant medications.

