### 6.6.1 Treatment of Infusion Reactions

In case of hypersensitivity reactions, the Investigator should institute treatment measures deemed medically appropriate in accordance with current medical practice and treatment guidelines. The following treatment recommendations are based on prior experience with Taxol (containing Cremophor); these and/or other measures deemed medically necessary should be implemented based on the judgment of the Investigator. To reduce the risk of infusion reactions caused by Cremophor, premedication with H1- and H2-blockers (diphenhydramine and ranitidine or equivalents) or dexamethasone (Refer to Section [7.1.2](#) for additional instructions on premedication with steroids) will be given.

Note that the “Grades” listed below do not correspond to NCI CTCAE v5.0 criteria (which are based on response to intervention, and thus are not used here to recommend specific interventions). For the purpose of AE reporting and for determining the need for dose modifications, NCI CTCAE v5.0 grading for allergic reaction should be used.

- Grade 1 allergic reaction/hypersensitivity (e.g., transient flushing, rash, drug fever < 38°C):
  - Supervise at the bedside.
  - Report to Sponsor as an adverse event of special interest (AESI)
- Grade 2 allergic reaction/hypersensitivity (e.g., urticaria, drug fever ≥ 38°C, rash, flushing, dyspnea):
  - Interrupt the infusion and disconnect infusion tubing from patient,
  - Administer IV antihistamines (diphenhydramine 25 to 50 mg), and ranitidine,
  - After recovery from symptoms, resume the infusion at a half of the infusion rate and if no further symptoms appear, complete the administration of the dose. A target infusion time of up to 3 hours may be appropriate in many cases.
  - Report to Sponsor as an AESI
- Grade 3 or 4 allergic reaction/hypersensitivity (e.g., symptomatic bronchospasm requiring parenteral medication(s) with or without urticaria; allergy-related edema/angioedema; anaphylaxis; hypotension):
  - Stop the infusion and disconnect infusion tubing from patient,
  - Administer epinephrine, antihistamines, and nebulized bronchodilators as medically indicated,
  - Consider IV steroids which may prevent recurrent or ongoing reactions,
  - **Report to Sponsor as a serious adverse event (see Section [8.2](#)),**
  - Also report to Sponsor as an AESI

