### 8.4 ADVERSE EVENTS OF SPECIAL INTEREST

An adverse event of special interest (AESI) is one of scientific and medical interest specific to understanding of the Investigational Product and may require close monitoring and rapid communication by the investigator to the Sponsor. An AESI may be serious or non-serious. The rapid reporting of AESIs allows ongoing surveillance of these events in order to characterize and understand them in association with the use of this investigational product. AESI for AL101 include events that are mediated by disruption of the Notch signaling pathway and can be attributed to the drug's mechanism of action with no clear alternate etiology and which may require more frequent monitoring and/or interventions. All AESI must be reported in the AESI section of the CRFs.

AESI observed with AL101 are detailed in the sections below and include hepatic function abnormalities, colitis, infusion reactions (including anaphylaxis), keratoacanthoma, and potential drug-induced liver injury (DILI). For dose modifications and toxicity management for the AESI, please refer to Section 6.6.

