#### 8.4.2 Colitis

In study CA216001, DLTs consisting of Grade 3 colonic ulceration/Grade 3 diarrhea were reported, both indicating the potential for development of colitis. Intestinal inflammation is thought to be an on-target effect that requires close monitoring and potential dose reductions. Intense abdominal pain, severe diarrhea and the presence of blood and/or mucous in the stools are indicative of potential colitis. Signs and symptom of colitis should prompt work up to rule out an infectious etiology. The gold standard for the diagnosis of colitis pathological and thus requires a biopsy, but in the absence of an infectious etiology, colitis should be the exclusion diagnosis. For management of colitis see Table 10.

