Adverse Events (CTCAE), version 5.0 (Nov 2017). Grades will be presented as mild (Grade 1), moderate (Grade 2), severe or medically significant (Grade 3), life-threatening (Grade 4) or death (Grade 5).

Adverse events of special interest (AESI) include hepatic function abnormalities (hepatotoxicity), colitis, infusion reactions (including anaphylaxis), Keratoacanthoma and potential drug-induced liver injury (DILI).

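### The AESI tables have no category-level patient count, so an AESI reported under several preferred terms, chiefly infusion reactions, has no single incidence by dose cohort

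*SAP*

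**What the plan says.** SAP 6.4.2.1 names five categories: "Adverse events of special interest (AESI) include hepatic function abnormalities (hepatotoxicity), colitis, infusion reactions (including anaphylaxis), Keratoacanthoma and potential drug-induced liver injury (DILI". Protocol 8.4 names the same five and gives them their own place in data capture: "All AESI must be reported in the AESI section of the CRFs".

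The SAP plans two AESI tables in 7.8.2. One is "Subject incidence of AESIs by MedDRA system organ class and preferred term". The other is "Subject incidence of AESIs related to investigational product and MedDRA system organ class and preferred term". Section 7.8.2.1 repeats the structure, "AESIs will be summarized by subject incidence by MedDRA system organ class and preferred term", and adds a separate listing. The counting rule in 7.8.2 counts a patient once per level and gives as example levels any event, system organ class (SOC) and PT. Neither the SAP text nor Protocol 9.7 gives a category level or a list of terms per category. Several other tables in 7.8.2 are split by grade or restricted to Grade 3 and above; the AESI tables are not.

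Liver injury is also summarised outside the adverse event tables. SAP 7.8.4 plans the number and percentage of patients meeting Hy's Law at each visit, and shift tables from baseline to worst CTCAE grade for each gradable laboratory test.

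**The concern.** AESIs are defined one way and tabulated another. The definition is by type of harm; the table is by coded term. If one type of harm arrives under several terms, its patients are split over rows, and no row gives the number of distinct patients.

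This matters most for the dose question. Protocol 1.4.1 supports the 6 mg cohort by reference to toxicity management for gastrointestinal and liver events, and points to the liver AESI sections. It also records that the previous developer recommended 4 mg as the maximum tolerated weekly dose in solid tumors. The incidence of each AESI category in each cohort is therefore a figure that a reader of the study report will look for. If it is not planned, someone will derive it afterwards, choosing the terms with the data in view. SAP section 4 says that avoiding decisions of that kind is a purpose of the SAP.

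**Working it through.** The plan states no figure on this point, so there is none to reproduce. The check compares definitions with tables and then applies a counting bound.

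**1. Which categories can spread over several terms?**

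- *Infusion reactions.* The documents use at least four labels: allergic reaction/hypersensitivity (Protocol 6.6.1), infusion-related reaction (Protocol Table 6), anaphylactic reaction (Protocol 1.4.1, from CA216001) and infusion site reactions (Protocol 1.3.2, from this study). Whether the last belongs in the category is exactly what a term list or eCRF category would settle. The spread arises without assuming that single symptoms are coded separately.
- *Hepatic function abnormality.* Protocol 8.4.1 defines it by two laboratory findings together. Protocol 1.4.1 reports a component term, AST increased, from CA216001.
- *Colitis and keratoacanthoma.* Each can map to a single PT. Where it does, the PT row counts each patient once and is the category count.

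**2. What can be read from PT rows?**

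Let a category be split over PTs with n1, ..., nk patients in a cohort of N. The number of distinct patients D satisfies

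max(ni) ≤ D ≤ min(N, n1 + ... + nk).

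The lower limit holds when every patient also appears in the largest row; the upper limit when no patient appears twice. With k = 1 the limits coincide. The SOC row settles D only if all the category's terms fall in one SOC and no other AESI does.

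Illustration, with assumed counts: N = 42 (the Cohort 2 maximum), and three PTs with 3, 2 and 2 patients.

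- Lower limit: 3/42 = 7.1%.
- Upper limit: (3 + 2 + 2)/42 = 7/42 = 16.7%.
- Width: 4/42 = 9.5 percentage points.

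**3. Do the liver summaries in SAP 7.8.4 supply the liver count?**

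| | Protocol 8.4.1 | SAP 7.8.4 Hy's Law |
|---|---|---|
| ALT or AST | > 3 x ULN | > 3 x ULN |
| Total bilirubin | > 2 x ULN | > 2 x ULN |
| ALP | no condition | < 2 x ULN |
| Timing | same draw, or draws within 8 days | no rule stated |
| Count | not specified | per visit |

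Three differences follow.

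- A patient who meets the two shared thresholds with ALP at or above 2 x ULN is in the protocol category but not in the SAP table.
- Liver tests are weekly until week 32 (Schedule of Activities, note h). Two consecutive weekly draws are nominally 7 days apart, inside the 8-day window, so findings split across adjacent visits can qualify under the protocol. A visit-by-visit table does not capture this unless a rule is added.
- A patient who qualifies at several visits is counted at each, so the visit counts do not add up to the number ever affected.

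The shift tables treat one test at a time and cannot show two elevations together.

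**The case against.** A reader might infer that no planned table gives the number of patients with colitis, an infusion reaction or hepatotoxicity. The documents do not support that. Any event coded to colitis or keratoacanthoma has a distinct-patient PT row, and SAP 7.8.4 counts patients with liver injury on laboratory criteria.

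A reader might also take the signs in Protocol 6.6.1, such as "Grade 2 allergic reaction/hypersensitivity (e.g., urticaria, drug fever", as separate terms that will each be coded. They are examples of signs used to guide management. The same section directs sites to CTCAE grading for allergic reaction when reporting, so a reaction may well be recorded as one event. Nor does Protocol 8.4.2 call diarrhea colitis. Its words are "DLTs consisting of Grade 3 colonic ulceration/Grade 3 diarrhea were reported, both indicating the potential for development of colitis", which describes a warning sign. Pooling diarrhea with colitis could inflate the rate.

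It is likewise not generally true that each PT row understates its category and that the sum overstates it. The first needs several terms in use; the second needs patients with more than one term.

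Further points against: the study is non-comparative; no AESI rate is a named endpoint; Protocol 9.7 itself plans adverse event summaries by SOC and PT. AESIs have a listing from which at most 45 + 42 = 87 planned patients could be counted by hand. SAP section 4 also refers to table templates that are not in the public text.

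These points narrow the concern and show that no data are lost. They do not remove it. The four labels remain. A listing leaves the choice of terms open until after lock, and the SAP text itself specifies no category row.

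**Conclusion.** The point holds as a gap in the planned safety reporting. For an AESI reported under more than one PT, chiefly infusion reactions and hepatic abnormalities, the plan gives limits rather than an incidence by dose cohort, and no grade for the category. For a category with a single PT nothing is missing. The liver summaries are useful but do not give the count under the Protocol 8.4.1 definition.

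The size cannot be stated from the documents, because they contain no coded AESI counts by PT for the two cohorts. The range of 7.1% to 16.7% rests on assumed counts and shows only how wide the limits can be. The conclusion assumes that at least one category is coded to several PTs and that the unpublished templates do not already contain category rows. The change is worth making because it is cheap and fixes the definitions before lock; no efficacy conclusion depends on it.

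**What to change.** In SAP 7.8.2 and 7.8.2.1, for both AESI tables (all and related):

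- Add one row per AESI category, by cohort, counting each patient once at worst grade, with PTs nested beneath.
- Take the category from the AESI section of the eCRF. If the form holds only a flag, fix a list of PTs per category before database lock and attach it to the SAP.
- State how a patient who meets both the hepatic-abnormality and the potential-DILI category is counted: for example, in both rows with the overlap footnoted, or in one combined liver row.
- Do not move diarrhea or other non-colitis terms into colitis unless the site reported the event as that AESI.
- Keep the SOC and PT table as supportive.

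The cost is SAP wording and one grouping variable in two tables already planned, using data already collected. The one downside is a single assignment of terms to categories if the eCRF does not record them. SAP section 4 notes that the plan was itself revised between the dry run and database lock, so a change of this size fits the way the document has been managed. No clinical rule is affected.
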